### **Informed Consent**

Participants will first read about the study rationale and procedure, and then will be told the following during informed consent: 1) the potential risks and benefits of the interventions, 2) safety arrangements that have been put in place for them during and after the study, 3) the circumstances under which they should contact a professional from an emergency list that will be accessible at all times via the menu item “Help Me” on the intervention website, and 4) that participation is voluntary and they are free to withdraw from the study at any time without penalty. As previously mentioned, participants endorsing significant suicide ideation and/or plans will be told to visit a hospital or other resources for support immediately. Following informed consent, participants will be able to register on the intervention website where they will have access to the treatment modules.

Participants will not be able to participate until they have provided informed consent. Participants will provide electronically recorded informed consent through the treatment website. They will be taken to this page by receiving a link from the researchers. The website will first show a brief version of the consent form with the main components highlighted. However, participants will be provided with a downloadable version of the consent form on this same page as well. They will be told to download and read the entire version in full before signing it. They will also be encouraged to save this copy of the form. The goal of this procedure is to reduce space on the website page as well as increase the likelihood of the participant retaining a copy for their records. This procedure is being utilized by our colleagues in Switzerland, as well as in similar online self-help programs around the world.

After they have provided informed consent, they will be invited to create login information on the treatment website, and from there will complete the baseline assessment measures to determine eligibility. Therefore, we will not obtain information from individuals who do not consent to participate. After the completion of baseline measures, participants that are deemed eligible will be given access to the intervention. In other words, consent will be obtained from the participant prior to the baseline assessment. Should participants have any questions about the study before and/or after completing it, the name and contact information of the Principal Investigator, [name], will be included on the consent form. Participants are encouraged to delay their participation until their research related questions have been asked and answered.

### **Risks and Benefits**

*Possible Risks:* There are increased risks associated with recruiting young adults with alcohol misuse and emotional symptoms. We would expect higher base rates of suicidal ideation and self-harming behaviours in these individuals relative to those without these mental health

concerns. Therefore, we will have safeguards in place in order to minimize the risk of harm. Young adults who report significant suicide ideation and/or plans during screening will be given a recommendation to visit their local medical professional (GP or hospital) for support as soon as possible. We will also be monitoring changes in suicidality at three time points, and will direct participants to emergency services if needed. Supports will also be accessible to participants at all times via the menu item “Help Me” on the intervention website. This will include a list of mental health services, including community resources, public and private psychologists, hospitals, and helplines. Participants in the control condition (psychoeducational) will be given access to the active treatment after the final assessment (6-months). They will receive all elements of the integrated intervention. While there is a risk that the content may be potentially distressing to some participants, resources will be provided as safeguards in order to mitigate these feelings of distress.

*Possible Benefits:* There are also potential benefits to participating in the current research. By working through the 12 modules, participants will be provided with the skills to cope with emotional challenges that are often triggers for alcohol use. The development of protocols is empirically informed, and there is a strong evidence base suggesting their success. Thus, completing each module throughout treatment stands to elicit a reduction in symptoms of both alcohol misuse and emotional problems. Furthermore, the proposed intervention stands to benefit Canadians as a whole by offering a potentially successful and cost-effective treatment option by which to improve their mental health. By offering the program online, we will be able to reach Northern and rural communities who otherwise may not have had access to treatment. By offering this widespread treatment in a user-friendly manner (i.e., online), participants also stand to benefit from access to treatment without any stigma, which is a known barrier to accessing treatment among substance users (Livingston, Milne, Fang, & Amari, 2012). Additionally, the program is being offered free of charge, when standard rates of therapy are as high as \$180/hour. Finally, the proposed treatment may provide an opportunity for early intervention to a population that is already struggling.

### **Anonymity and Confidentiality**

In order to determine who is eligible to participate in the study, potential participants will need to create a unique username to access the program. Outside of this username, no identifying information will be collected on the study website. Therefore, the only potentially identifying information collected would be if participants create a username using their first and last name. Eligible participants will also be given a unique participant ID. Participant ID numbers will be automatically generated by the study website immediately after registration using an incremental number system. The data collection file will contain these participants ID's and scores on each measure, but will not contain identifiable information (i.e., usernames). The data file used for statistical purposes will remain completely anonymous at all times. The de-identified raw data will be retained indefinitely for dissemination purposes/meta-analyses in order to inform future research. While we will be using e-mail addresses to contact interested participants this information will never be recorded nor linked to their data. All study data will be automatically collected on the website without identifying information.

Since we will not be collecting identifying information, no formal records of client data will be retained. The only data retained will be the scores to questionnaires obtained through the study

website itself. Furthermore, while the program was designed using in-person treatment methods, it is ultimately a self-help program. Therefore, it is not necessary nor feasible to make a client record for each participant given the nature of the self-guided program as well as the lack of identifying information being obtained.

Only primary researchers and coaches will have access to the e-mails received by participants who decide to contact their e-coach. These e-mails will come to the e-mail address affiliated with the treatment website, and for which only coaches and primary researchers will have access. Although limited identifying information will be collected from participants, [name], his graduate students, and all other research assistants involved in the project will complete PHIA training and sign a pledge prior to becoming involved in the research. [name] and the two primary graduate students involved in the project (i.e., the Research Assistants who will also be acting as e-coaches) have already signed this pledge. The only potential breach of confidentiality will be if clients accidentally leave their computer screen open in a public space with the clinical trial open on the desktop. In order to mitigate this, the treatment website will automatically log the participant out after they have been inactive for 20 minutes. Limits to confidentiality will be: if the participant poses an imminent risk to themselves or another individual, if issues surrounding child welfare are disclosed, or if the researchers are legally subpoenaed. All participants will be made aware of issues surrounding confidentiality in the consent form.

Results of the study will only be presented at the aggregate level - individual data will not be reported or presented. Data will be collected on the treatment website. Further, data will be kept and analyzed on a password-protected computer in [name] locked laboratory. Only [name] and members of his laboratory will have access to the data for projects and theses.

### **Compensation**

Participants will be compensated with a \$30 Amazon gift card for completing all three assessments (\$10 per assessment).

### **Dissemination**

The results of this study will be presented at academic conferences and published in peer-reviewed journals on addictive behaviours. Results will only be presented at the aggregate level, and individual data will not be presented. This will inform both research and practice by making the findings accessible to academics, practitioners, and the general public. Results of this study may have implications for the clinical treatment of alcohol misuse and emotional problems among adults. Specifically, if effective, this study will demonstrate the effectiveness of a novel integrated treatment for individuals suffering from alcohol misuse and comorbid emotional disorders, and thus offer a feasible treatment options for said individuals.

## Statistical Analysis Plan

**Power Analysis:** A recent meta-analysis showed that combined CBT/MI resulted in statistically significant reductions in alcohol use and depressive symptoms, with effect sizes being in the small range in both clinical and subclinical groups ( $g=.17-.27$ ). Data show relatively comparable effect sizes for online and in person interventions for alcohol misuse and depression. Therefore, a small effect size ( $g=.25$ ) is expected for group differences in alcohol use and emotional symptoms at posttreatment. Using G\*Power, the required sample size to detect a small effect size is  $N=398$  (with power rate set at .80 and  $\alpha = .05$ ).

**Statistical Plan:** Before hypothesis testing, we will run preliminary analyses (e.g., baseline differences, missing data analyses). We will also examine overall group differences in clinically meaningful variables (i.e., % below moderate cut-offs on the AUDIT, CES-D, and GAD-7 after treatment and at follow-up). Next, Generalized Estimating Equations (GEE) will be used to evaluate the main hypotheses that integrated treatment will result in the largest reductions in alcohol use, depression, and anxiety. GEE is a multilevel modeling technique that is preferable to repeated-measures ANOVA for pre/post analyses, as it will allow us to include all randomized participants in analyses. This results in less bias due to missing follow-up data. However, due to potential attrition problems, we also plan to conduct a sensitivity analysis. Primary and secondary outcomes will be tested sequentially in a mixed within- (repeated assessments) and between-subjects (treatment condition) design.

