## **Participants**

A target sample of 400 participants will be recruited for the study. Participants will include Canadian young adults struggling with moderate alcohol misuse and emotional problems. Inclusion criteria will include: 1) individuals between 18 and 35 years old, 2) reporting difficulties with alcohol indicated by a score  $>3$  for women and  $>4$  for men on a brief version of the Alcohol Use Disorders Identification Test [AUDIT; Saunders et al., 1993] known as the AUDIT-C, 3) reporting depression and/or anxiety symptoms indicated by a score  $>16$  on the Center for Epidemiological Studies Depression Scale [CES-D] and/or a score of  $>5$  on the Generalized Anxiety Disorder Scale-7 [GAD-7], 4) fluency in English, and 5) have weekly Internet access. Exclusion criteria will include the following: 1) self-reported engagement in other psychological or pharmacological treatments for alcohol misuse and/or depression/anxiety; 2) elevated suicidality (defined as scoring greater than "minimal risk" on a screener); and 3) current psychosis or mania. Interested participants will be invited to contact the primary investigators for a link to the study website. Participants will be sent a link with information about the study and be able to provide informed consent electronically directly on the treatment website. They will also be provided with detailed instructions on how to create a user account for the self-help program, and be encouraged to contact the researchers should they have any trouble at this stage. After they have provided informed consent, they will be able to register on the study website. They will need to create a username as well as verify their account via e-mail before they can access the website. After informed consent has been obtained and their account has been verified, they will immediately be asked to complete the baseline assessment measures. If they are eligible, they will be able to access the 12 treatment modules and continue with the study procedure. Interested adults with clinically-elevated symptoms (i.e., those who score above the cut-offs on our screening tools) will be still given access to the integrated intervention, and will be given the contact information for a mental health professional in their area. However, they will be excluded from the study and their data will not be tracked.

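### The 80% power behind N=398 is tied to no stated test: 398 fits a one-sided t-test, while a two-sided unadjusted comparison at 400 has about 70% power even with complete data

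*SAP*

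**What the plan says.** The SAP (Statistical Analysis Plan, Power Analysis) takes g=.25, which "is expected for group differences in alcohol use and emotional symptoms at posttreatment", sets power at .80 and alpha at .05, and reports from G*Power that "the required sample size to detect a small effect size is" 398. The Protocol (Participants) states: "A target sample of 400 participants will be recruited for the study". Allocation is 1:1 (Protocol, Method).

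The SAP's Statistical Plan then describes a different kind of analysis. GEE will address the "main hypotheses that integrated treatment will result in the largest reductions in alcohol use, depression, and anxiety", and "Primary and secondary outcomes will be tested sequentially in a mixed within- (repeated assessments) and between-subjects (treatment condition) design". On missing data, the SAP favours GEE because "it will allow us to include all randomized participants in analyses", and adds that "due to potential attrition problems, we also plan to conduct a sensitivity analysis". The Protocol (Compensation) offers an "Amazon gift card for completing all three assessments", paid per assessment.

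Neither document states whether the test is one- or two-sided, which G*Power procedure was used, what within-person correlation was assumed, or what proportion is expected to be assessed at T1 (end of the 8-week treatment) or T2 (24 weeks).

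**The concern.** A sample size cannot be checked without the test and its sidedness, and here the choice matters: the usual two-sided t-test for g=.25 needs over 100 more participants than the plan states. One-sided .05 is equivalent to two-sided .10. If sidedness is not fixed in advance, the criterion for a positive primary result can be chosen after the data are seen.

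The target also exceeds the required number by only 2, although the SAP itself expects attrition. A null result would be read against an 80% that may not apply. Nor is that 80% linked to any contrast of the GEE that will actually be run.

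**Working it through.** **Inputs from the documents.** d=.25 (SD taken as 1), alpha .05, power .80, 1:1 allocation, N=398, target 400. **Assumed, because the documents give nothing:** missingness at T1, within-person correlation ρ, exchangeable correlation structure, equal variances.

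**1. Reproducing 398.** For two independent means, n per arm ≈ 2(z_alpha + z_power)²/d².

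- One-sided .05: 2(1.645+0.842)²/.0625 = 197.9. The exact noncentral t gives 198.5, so 199 per arm = **398**.
- Two-sided .05: 2(1.960+0.842)²/.0625 = 251.2. The exact noncentral t gives 252.1, so 253 per arm = **506**.

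**2. Other routes to 398, two-sided.**

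- G*Power's repeated-measures between-group test with f = d/2 = .125 and m assessments scales N by (1+(m−1)ρ)/m. Setting 506 × (1+(m−1)ρ)/m = 398 gives ρ≈.57 for m=2 and ρ≈.68 for m=3. At ρ=.5 the test gives 380 (m=2) or 338 (m=3).
- Baseline adjustment scales N by (1−ρ²): ρ = √(1−398/506) ≈ .46.

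All of these need a correlation that is not stated. The one-sided t-test needs no further input.

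**3. Unadjusted T1 comparison.** At 200 per arm the noncentrality is .25×√(200/2) = 2.5. Noncentral-t power:

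| Missing at T1 (assumed) | N assessed | Two-sided | One-sided |
|---|---|---|---|
| 0% | 400 | .703 | .803 |
| 10% | 360 | .657 | .765 |
| 20% | 320 | .606 | .721 |
| 30% | 280 | .550 | .671 |
| 40% | 240 | .488 | .613 |

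The effect detectable with 80% power at N=400 is .281 two-sided and .249 one-sided. Keeping 80% one-sided needs 398/400 = 99.5% assessed.

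**4. Repeated-measures model keeping all randomised participants.** Generalised least squares on T0, T1 and T2, two-sided, with power = Φ(.25/SE − 1.96). *Adjusted* means a common baseline mean; *change* means the group difference in T1−T0. With r = ρ/(1+ρ), the partial correlation of T1 and T2 given T0, the squared standard errors are:

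- Complete data: adjusted (2/200)(1−ρ²); change (2/200)·2(1−ρ).
- 30% missing at T1, T2 also missing: adjusted A = (2/140)(1−ρ²).
- 30% missing at T1, T2 observed: adjusted A = 2(1−ρ²)[(1−r²)/140 + r²/200].
- Change with 30% missing: A + 2(1−ρ)²/200, using the matching A.

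Example at ρ=.5, complete data: adjusted SE = √.0075 = .0866, .25/.0866 = 2.887, power Φ(0.927) = .823. Change SE = .1, power Φ(0.540) = .705.

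| Two-sided power | ρ=.3 | ρ=.5 | ρ=.7 |
|---|---|---|---|
| Adjusted, complete | .746 | .823 | .938 |
| Change, complete | .561 | .705 | .898 |
| Adjusted, 30% missing | .592–.599 | .676–.690 | .834–.852 |
| Change, 30% missing | .464–.468 | .585–.597 | .789–.807 |

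Lower ends have T2 also missing; upper ends have T2 observed. The noncentral t changes the complete-data rows by at most .002.

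**5. What keeping everyone recovers.** At ρ=.5 with 30% missing, T1 completers alone (N=280) give .673 adjusted and .550 change. The all-randomised model gives .676–.690 and .585–.597, a gain of 0–2 and 4–5 points.

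**6. Correlation needed for two-sided 80% at 400.** Complete data: about .46 adjusted, .60 change. With 30% missing: .65–.67 adjusted, .69–.71 change.

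**The case against.** The best defence is that 398 is not an arithmetic error. At least one standard calculation reproduces it exactly, and matching a one-sided t-test does not prove that one was used. A two-sided baseline-adjusted analysis reaches 80% with a correlation of only about .46, and at .5 it has 82% with complete data. The SAP plans GEE, not an unadjusted T1 test, so 70% is a benchmark and not the trial's power. The SAP does state alpha; only its sidedness is missing. Retention is also not ignored: besides the payment, the Protocol (Method) describes reminders, progress feedback and e-coaches in the active arm, intended partly to limit dropout.

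Most of this stands as a limit on the claim. The one-sided setting is inferred, the directional hypothesis makes it possible without declaring it, and GEE power may be above or below 80%. It does not rescue the stated figure. Each two-sided route depends on a correlation the documents never give, and the favourable 82% assumes nobody is lost. The retention measures come with no rate. Including all randomised participants deals mainly with bias; it recovers only a few points of the power lost when T1 is missing.

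**Conclusion.** The concern holds. For the unadjusted T1 difference at g=.25, the target of 400 delivers 80% only under an undeclared one-sided .05 test with no more than 0.5% loss. Two-sided it delivers about 70% with complete data, and 55% if 30% are missing. For a repeated-measures analysis the two-sided figure lies anywhere from about 46% to 94% over correlations of .3 to .7 and 0% to 30% missing, so the 80% cannot be confirmed or excluded.

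The 398, 506 and 70% figures rest only on the SAP's own inputs and the choice of sidedness. The wider range rests on the assumed correlations, missingness, exchangeable structure and equal variances. Nothing here biases the effect estimate or invalidates the trial, but the power statement should be corrected.

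**What to change.** Keep the target of 400. In the SAP:

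- Name the G*Power test behind 398. Declare the primary test either two-sided at .05, or openly one-sided at .05 with the statement that this equals two-sided .10.
- If two-sided, replace the 80% with about 70% for the unadjusted T1 comparison with complete data (detectable g=.28), or claim power for a named GEE or baseline-adjusted contrast over a stated range of correlations, for example .3 to .7.
- In either case, state the expected T1 retention and the power at that retention.

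This changes wording only, with no extra participants and no change of procedure. The price is a less favourable stated power, or a one-sided test that has to be openly declared.

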depression severity (Radloff, 1977). Anxiety symptoms will also be assessed at all three assessment points using the GAD-7, a 7-item self-report questionnaire used to measure the severity of anxiety symptoms (Spitzer, Kroenke, Williams, & Löwe, 2006). In order to determine clinically significant and combined reduction in alcohol use and comorbid emotional problems, we will use a combined outcome of alcohol use on the AUDIT, and cut-offs from the GAD-7 and CES-D. We will also measure participants' quality of life using the World Health Organization Quality of Life assessment (WHOQOL-BREF). This is a 26-item self-report measure that assesses functionality in various life domains (The WHOQOL Group, 1998). A sum score will be used to assess overall quality of life at all assessments points (i.e., T0-T2). We will also collect information on participants' use of other substances using the National Institute on Drug Use (NIDA ASSIST; National Institute on Drug Abuse, 2009), and their executive functioning using the WebEx (Buchanan et al., 2010). This information will be collected to examine transfer effects to other substances, as well as to examine the potentially moderating effects of executive functioning. Finally, we will obtain a measure of participants' level of motivation in terms of importance, confidence, and readiness. Participants will complete all measures at each of the three time points, with the exception of the Demographics questionnaire and the AUDIT, which will only be completed at baseline.

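### The percentages below the CES-D and GAD-7 cut-offs include people who were never above them at entry, so they describe end states and cannot be read as reduction without a baseline condition

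*SAP*

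**What the plan says.** **Entry.** Protocol, Participants, admits people "reporting depression and/or anxiety symptoms indicated by a score" above 16 on the CES-D and/or above 5 on the GAD-7. One raised scale is enough. The alcohol criterion uses a short form, "known as the AUDIT-C".

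**Outcome.** SAP, Statistical Plan, lists as clinically meaningful variables the percentage "below moderate cut-offs on the AUDIT, CES-D, and GAD-7 after treatment and at follow-up". It gives no cut-off values, no requirement to have been above a cut-off at T0 and no adjustment for baseline status. GEE is then used for the main hypotheses on alcohol use, depression and anxiety.

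**Stated purpose.** Protocol, Method (Research Instruments), describes a "combined outcome of alcohol use on the AUDIT, and cut-offs from the GAD-7 and CES-D", meant to show "clinically significant and combined reduction in alcohol use and comorbid emotional problems". It gives neither values nor a rule for joining the scales.

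**Schedule.** The same section has all measures completed at every time point, "with the exception of the Demographics questionnaire and the AUDIT, which will only be completed at baseline".

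**The concern.** Someone enrolled on depression alone can have a GAD-7 score at or below 5 on day one. If the score stays there, that person adds to the favourable GAD-7 percentage at T1 and T2 with no change. The same holds in reverse for someone enrolled on anxiety alone.

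The entry rule guarantees that each participant is raised on at least one scale, not on the scale being scored. If the moderate cut-offs are higher than the entry cut-offs, some participants could start below both.

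At stake is what the percentages mean. The protocol speaks of clinically significant reduction, whereas the SAP quantity is a share of people in a given state at a given time. A reader who takes 52% below the cut-off as 52% improved would be misled in both arms.

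**Working it through.** **1. The plan's own figure.** SAP, Power Analysis: a g of .25 "is expected for group differences in alcohol use and emotional symptoms at posttreatment", power .80, alpha .05, N = 398. A one-sided two-sample t-test gives 199 per arm, which is 398 exactly. A two-sided test gives 253 per arm, or 506. The SAP does not state sidedness. The figure is for a continuous difference; no sample size is given for the cut-off percentages.

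**2. Share already below one cut-off at entry (q).** The documents do not give it, so it has to be assumed. Let C and G mean raised on CES-D and on GAD-7. Then

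q(CES-D) = P(not C, G) / P(C or G).

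Example: each scale raised in 50% of applicants, bivariate normal, correlation .5. P(C and G) = 1/4 + arcsin(.5)/(2π) = 1/3. P(C or G) = 1 − 1/3 = 2/3. P(not C, G) = 1/2 − 1/3 = 1/6. So q = (1/6)/(2/3) = 25%. With correlation .8, q is 17%. With unequal prevalence (CES-D raised in 30%, GAD-7 in 50%, correlation .5), 48% start below the CES-D cut-off and 13.5% below the GAD-7 cut-off. Over all the settings tried, q for a single scale ran from 2% to 63%. The share at or below both entry cut-offs is 0 by the entry rule.

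**3. What the percentage becomes.** Let p0 and p1 be the proportions falling below the cut-off among those raised at baseline (control, treated). Let s0 and s1 be the proportions staying below among those already below. Then

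- control: q·s0 + (1−q)·p0
- treated: q·s1 + (1−q)·p1
- difference: (1−q)(p1−p0) + q(s1−s0)

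Assume p0 = .40 and apply the SAP's effect as a probit shift: p1 = Φ(Φ⁻¹(.40) + .25) = .499. With q = .20 and s0 = s1 = 1:

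- control: .20 + .80 × .40 = .52
- treated: .20 + .80 × .499 = .599
- difference: .80 × 9.9 = 7.9 points

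Both levels rise and the difference shrinks. The shrinkage comes from setting s1 = s0. If treatment also prevents worsening in those already below, q(s1−s0) is positive and restores part of the difference.

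**4. Power.** Two-sided .05, 200 per arm, no attrition: power = Φ[(d − 1.96·se0)/se1], with se0 the pooled and se1 the unpooled standard error. The restricted analysis uses 200(1−q) per arm. With p0 = .40:

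| q | All randomised, s0 = s1 = 1 | All randomised, s0 = .85 and same .25 shift | Raised at baseline only |
|---|---|---|---|
| .2 | .355 | .431 | .426 (160 per arm) |
| .3 | .294 | .400 | .381 (140 per arm) |
| .4 | .241 | .374 | .335 (120 per arm) |

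In the middle column s1 = Φ(Φ⁻¹(.85) + .25) = .901. With nobody already below, power is .51. With p0 from .30 to .50 and q from .1 to .4, restriction adds about 3 to 12 percentage points if those already below all stay below, and roughly nothing if they share the benefit and 85% of controls stay below. If 95% of controls stay below and the benefit is shared, the results lie in between: .39 against .43 at q = .2.

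With a larger assumed effect (45% against 30% among those raised, a probit shift of 0.40) and q = .2, power is .67 in everyone against .79 restricted if those already below gain nothing. It is .77 against .79 if they gain the same shift with s0 = .85.

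**The case against.** The strongest reply is that a comparison of end states in everyone randomised is valid and fits the SAP's aim of including all randomised participants. The percentages are only something the team will also examine; change in alcohol use, depression and anxiety is tested by GEE. All of that stands. It limits the point to interpretation and to these secondary percentages.

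Three stronger readings are tempting, and the documents do not support them.

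- **The comparison is biased.** It is not. Baseline status is fixed before randomisation and balanced in expectation.
- **The combined outcome counts unchanged people as successes.** If it requires every scale to be at or below the entry cut-offs, nobody starts as a success, because entry needs at least one raised scale. The problem arises only if its cut-offs exceed the entry cut-offs or if one scale is enough. The protocol settles neither, so what is missing there is a definition.
- **The plan loses power.** That holds only if those already below gain little from treatment. The documents give neither their share nor their expected course, and the middle column of the table shows no loss. The trial is also not sized on these percentages: at the SAP's effect size, neither analysis exceeds about 50% power in the cases computed.

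What survives is that nothing in the plan separates people who fell below a cut-off from people who were never above it.

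**Conclusion.** The point holds for the single-scale CES-D and GAD-7 percentages, as an inexpensive improvement. That some participants may start below one cut-off follows directly from the and/or entry rule; how many is unknown. Under the assumptions above (q = .20, all of them staying below, 40% of raised controls improving), the reported percentages would be 52% and 59.9%, against 40% and 49.9% among those who had something to lose. The effect on power runs from none to a material loss and should not be the reason for the change. The primary outcome (drinks in the past seven days) and the GEE analyses are unaffected.

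The AUDIT percentage and the combined outcome have a prior obstacle: the protocol collects the AUDIT at baseline only, while the SAP scores it after treatment and at follow-up. As written, neither can be computed at T1 or T2.

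**What to change.** In the SAP's Statistical Plan:

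1. State one numeric cut-off each for CES-D and GAD-7, say whether it equals the entry cut-off, and say on which side a score exactly at the cut-off falls.
2. For each of the two scales, compare arms at T1 and T2 on the percentage below the cut-off among randomised participants at or above that same cut-off at T0. The subset is defined before randomisation, so the randomised comparison is preserved.
3. Keep the all-randomised percentage alongside, adjusted for baseline status and labelled as an end-state comparison. Report the share already below at T0 by arm.
4. For the combined outcome, state the cut-offs, the joining rule and how baseline status enters. Reconcile the baseline-only AUDIT schedule with the SAP before relying on it or on the AUDIT percentage.

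Items 1 to 3 cost a few lines and no new data, since CES-D and GAD-7 are already collected at T0, T1 and T2. The price is a smaller denominator per scale (160 per arm instead of 200 if 20% start below, 120 if 40% do), and the two scales' percentages will refer to different subsets. Item 4 may require a change to the assessment schedule.
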